8.4.4.2 SERIOUS ADVERSE EVENT REPORTING

Detailed reporting procedures will be contained in the Study Operations Manual.

If an SAE occurs, the investigator will take appropriate action immediately to promote patient safety and will strive to identify the cause of the event.

All SAEs will be reported by the Investigator to the pharmacovigilance provider within 24 hours of first discovery using the SAE Report Form. The SAE Report Form will be sent by email or by fax to:

Pharmacovigilance Provider: Pivotal

Email: [contact]

SAE Fax line (North American sites): [name]

SAE Fax line (European sites): [contact]

The following minimum criteria must be provided when reporting an SAE:

- Patient's study ID number.
- Name of IMP.
- Description of the event or outcome that can identify the case as serious.
- Name and contact information of the reporter.

Follow-up information should be actively sought and submitted as it becomes available. Relevant eCRFs, such as demography, medical history and concomitant medications, as well as test results, consultant reports, a summary of the outcome of the SAE, and the investigator's opinion of the event's relationship to the IMP will be provided if and when available.

The sponsor will also perform an evaluation of all SAEs.

The relevant health authorities and Central ECs/IRBs will be notified of any suspected unexpected serious adverse reactions (SUSARs) by Xenon (or designee) within the required reporting timelines (within 7 calendar days for fatal and life-threatening SUSARs, or 15 calendar days for all other SUSARs. Where applicable, the investigational sites will submit any reported SUSARs to their local ECs/IRBs upon receipt of the essential documents from Xenon (or designee).

8.4.4.3 REPORTING EVENTS TO PARTICIPANTS

Any new information about the IMP's safety or important information that becomes available during the study that may affect the patient's decision to continue their participation will be communicated to the patients in a timely manner, including a revision to the ICF.

8.4.4.4 EVENTS OF SPECIAL INTEREST

Not applicable.

8.4.4.5 REPORTING OF PREGNANCY

Pregnancy is not considered an AE, but patients will be instructed to report to the investigator if they/their partner become pregnant during the study or within 6 months after administration of the last IMP dose. The investigator should also be notified of pregnancy occurring during the study but confirmed after completion of the study. In the event that a patient/partner is subsequently found to be pregnant after the patient is included in the study, then consent will be sought from the partner and, if granted, any pregnancy will be followed, and the status of mother and/or child will be reported to the sponsor after delivery. Any patient reporting a pregnancy during the study will be discontinued from the study treatment and every reasonable effort will be made by the investigational site to follow the pregnancy until delivery.

All pregnancy notifications to the investigator must be reported to the pharmacovigilance provider (refer to the contact information in [Section 8.4.4.2](#)). Any pregnancy should be followed until the outcome of the pregnancy is known (spontaneous miscarriage, elective termination, normal birth, or congenital abnormality), even in the case when a male patient whose partner is pregnant discontinues the IMP or withdraws from the study. When the outcome of the pregnancy becomes known, an updated report should be submitted to the pharmacovigilance provider. If the study has completed by the time the outcome is known, the investigator should submit the updated report directly to the sponsor.

Male patients may continue in the study if an accidental pregnancy of their female partner occurs despite adequate contraception.

9 STATISTICAL CONSIDERATIONS

A formal statistical analysis plan (SAP) will be developed and finalized before database lock and will describe the participant populations to be included in the analyses, and procedures for accounting for missing, unused, and spurious data. This section is a summary of the planned statistical analyses of the primary and secondary endpoints. Formal analysis of the DBP will be executed upon completion of that component of the study. Analysis of the OLE will be executed separately and upon completion of that component of the study.

9.1 STATISTICAL HYPOTHESES

Primary Efficacy Hypotheses

The primary objective of this study is to assess the effect of 3 doses of XEN1101 on percent change in monthly focal seizure frequency from baseline to the DBP. The primary null hypothesis (H_0) is that all 3 dose groups are not different from placebo in median percent change in monthly (28 days) focal seizure frequency (MPC), with null hypothesis indicated below:

$$H_{0123}: MPC_{\text{plac}} = MPC_{10\text{mg}} = MPC_{20\text{mg}} = MPC_{25\text{mg}}$$

The alternative hypothesis is that there is a monotonic (non-decreasing) dose response trend for the 3 dose arms and the placebo. If the primary null hypothesis is rejected with 1-sided significance level of 0.05, the study will be considered positive with at least one dose better than placebo. Further hypotheses will be tested according the following hierarchy with the same 1-sided significance level of 0.05:

- Comparison between 25 mg versus placebo (H_{03} : $MPC_{plac} = MPC_{25mg}$).
- Comparison between 20 mg versus placebo (H_{02} : $MPC_{plac} = MPC_{20mg}$).
- Comparison between 10 mg versus placebo (H_{01} : $MPC_{plac} = MPC_{10mg}$).

The method for testing these null hypotheses for primary efficacy endpoint is described in [Section 9.4.2](#). This endpoint will be analyzed when all enrolled participants have completed the DBP, or been withdrawn from the study.

Key Secondary Efficacy Endpoint

The following null hypotheses apply to the key secondary endpoint:

- The proportion of responders (experiencing at least 50% reduction in focal seizure frequency [RR50]) in the DBP is the same in placebo and each dose group

The secondary endpoints will be analyzed when all enrolled participants have completed the DBP or been withdrawn from the study.

9.2 SAMPLE SIZE DETERMINATION

The sample size of 300 intent-to-treat (ITT) participants in the DBP will provide 88% power to reject the null hypothesis H_{0123} at a 1-sided 0.05-level, assuming $MPC_{plac} = -20\%$, $MPC_{10mg} = -25\%$, $MPC_{20mg} = -30\%$, $MPC_{25mg} = -35\%$. This assumed dose response and MPC is similar to [Porter et al. \(2007\)](#), with slightly higher placebo effect ([Khan et al., 2018](#)).

Study power was determined through 5000 simulated trials using R (v 3.5, R Core Team). Baseline and treatment seizure rates for each participant were randomly generated using a negative binomial distribution parameterized as a mixture of Poisson distributions with mean μ and variance $\mu + \mu^2/\theta$. Parameters μ and θ were selected to achieve a baseline seizure frequency of approximately 10 seizures per 4-weeks and on-treatment seizure frequency to achieve the target MPC. In repeated samples of $N = 100$, the Hodges-Lehmann estimate and associated 95% confidence intervals were comparable compared to those for similar MPC differences in [Porter et al. \(2007\)](#), confirming reasonable variance of the simulated participant-level MPC.

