4.3 SCIENTIFIC RATIONALE FOR STUDY DESIGN

Placebo is considered an appropriate control as all patients are required to be on at least one AED prior to screening and for the duration of the trial. Therefore, all patients will be receiving medication for control of seizures. An 8-week baseline period is required to establish seizure frequency for eligibility determination. An 8-week treatment period was chosen to establish efficacy for seizure suppression while minimizing time assigned to placebo treatment. The study design includes parallel enrollment into 3 dose groups in addition to the placebo arm. This parallel-group, dose-ranging, study design will enable exploration of the expected therapeutic range, including evaluation of the minimal effective dose. If the drug is found to be well tolerated and effective, this study will inform dose selection for confirmatory trials. The OLE will evaluate long-term tolerability, safety, and maintenance of efficacy of a 20 mg QD dose of XEN1101.

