9.4.2 ANALYSIS OF THE PRIMARY EFFICACY ENDPOINT(S)

The monthly (28 days) seizure rate will be calculated separately in the baseline and DBP as the total number of focal seizures reported \times 28 / the total number of days seizure information is available in that period. The countable seizures for the primary endpoint will include focal aware seizures with motor signs, focal seizures with impaired awareness with or without motor signs, and focal seizures that lead to generalized tonic-clonic seizures.

Percent change from baseline will be calculated as (post-treatment monthly [28 days] focal seizure frequency – baseline monthly (28 days) focal seizure frequency) / baseline monthly (28 days) focal seizure frequency, so that a more negative number will represent greater benefit.

Primary analysis to test the null hypothesis as described in [Section 9.1](#) is based on the ITT population. Since the endpoint of percent change from baseline in monthly seizure count tends to be not normally distributed, an analysis of covariance (ANCOVA) model for the ranks of monthly (28 days) focal seizure frequency percent change from baseline will be used as the dependent variable, with baseline monthly (28 days) focal seizure frequency rank, arm (placebo, 10 mg, 20 mg, 25 mg), region, and background use of CYP3A4 inducer medication included as factors.

Under the assumption of a monotonic dose response relationship (true effect for the higher dose is not worse than the lower dose), the null hypothesis (H_{0123} : $MPC_{plac} = MPC_{10mg} = MPC_{20mg} = MPC_{25mg}$) will be tested based on linear contrast for the least square means (with coefficient of -3, -1, 1, 3 for placebo and the 3 treatment levels of 10, 20, and 25 mg) within the framework of the ranked ANCOVA model. Since only a positive dose response trend is of interest to demonstrate treatment effect, a 1-sided test with significance level of 0.05 will be used.

If a significant result is achieved ($p < 0.05$) under H_{0123} , the study will be considered positive and at least one dose level of XEN1101 should be better than placebo.

After H_{0123} is rejected, further testing (with the same significance level of 0.05) will be performed to formally test the pairwise difference H_{03} : $MPC_{plac} = MPC_{25mg}$, H_{02} : $MPC_{plac} = MPC_{20mg}$ and H_{01} : $MPC_{plac} = MPC_{10mg}$.

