MPC_{10mg} in sequential order ($H_{03} \rightarrow H_{02} \rightarrow H_{01}$) to assess whether each dose level is significantly better than placebo in percent reduction of monthly focal seizure count, within the same ANCOVA model. To control the type I error, only when the early null hypothesis is rejected, then the later hypothesis can be formally tested.

On the other hand, if the primary null hypothesis H_{0123} is not rejected, then additional formal statistical testing will not be performed. However, the nominal p-value comparing each of the doses versus placebo will still be provided for exploratory purposes.

With this a-priori specified stepwise testing procedure, the overall type I error will be controlled at 0.05 (1-sided).

Note that this study was designed as a Phase 2 study; therefore, 1-sided alpha of 0.05 was proposed to determine the efficacy of XEN1101. Further study will be needed to confirm the efficacy of XEN1101. It is the sponsor's understanding that in order for this study to be considered as a pivotal study, the 1-sided p-value will need to be <0.025 in favor of XEN1101.

Additional sensitivity analyses for the primary endpoint will be specified in the SAP.

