9.4.3 ANALYSIS OF THE SECONDARY ENDPOINT(S)

Secondary analyses will be performed in the ITT population on data from the DBP as follows:

- **RR50 (Key Secondary Efficacy Endpoint):** The proportion of participants experiencing a monthly (28 days) focal seizure frequency improvement from baseline of $\geq 50\%$ will be compared using a logistic regression model with baseline monthly (28 days) focal seizure frequency, region, background use of CYP3A4 inducer medication and treatment included as factors. Pairwise comparisons will be performed to characterize the dose response. Odds ratios and their 95% confidence intervals will be calculated for each comparison.
- **Stability of Weekly Seizure Frequency:** Within study arm, the absolute and percent change in weekly focal seizure rate will be calculated for every week of the treatment period and a linear test for trend will be evaluated and estimated to determine whether there is an average increase or decrease over time. A quadratic and spline effect may also be estimated for each dose, if the linear model appears inadequate for the data.
- **Clinical and Patient Global Impression of Change:** Change scores in each dose group will be compared to placebo using an ANCOVA, including for rank of baseline seizure frequency, region, and background use of CYP3A4 inducer medication. Estimated medians, and Hodges-Lehman estimates statistics for differences, will be calculated.

Analysis detail on statistical testing for secondary endpoints will be provided in the SAP.

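### Does powering only the trend test, with no stated estimate for doses the sequence leaves untested, leave the plan short on 10 mg and 20 mg?

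*Combined protocol and SAP*

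**What the plan says.** Section 9.1 makes H0123 (placebo and all three doses equal) the primary null hypothesis and calls the study positive if it is rejected. Section 9.2 sizes the trial on that hypothesis: 300 ITT "participants in the DBP will provide 88% power to reject the null hypothesis" H0123 at one-sided 0.05, with assumed medians of -20%, -25%, -30% and -35% for placebo, 10, 20 and 25 mg. Neither theta nor an SD is given. The simulation was checked by noting that "the Hodges-Lehmann estimate and associated 95% confidence intervals were comparable" to those of a cited dose-ranging trial.

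Section 9.4.2 uses an ANCOVA "model for the ranks of monthly (28 days) focal seizure frequency percent change from baseline". The trend contrast comes first, followed by 25, 20 and 10 mg versus placebo in that order (H03, H02, H01) from the same model: "only when the early null hypothesis is rejected, then the later hypothesis can be formally tested". If H0123 is not rejected, formal testing ends, but "the nominal p-value comparing each of the doses versus placebo will still be provided for exploratory purposes". No sentence covers a stop at H03 or H02 after H0123 has been rejected.

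For secondary endpoints, section 9.4.3 is more explicit. For RR50, "Odds ratios and their 95% confidence intervals will be calculated for each comparison". For the global impression scales, "Estimated medians, and Hodges-Lehman estimates statistics for differences, will be calculated". Section 9.4.1 says all analyses will come with graphs, forest plots among them. Section 4.3 says the design "will enable exploration of the expected therapeutic range, including evaluation of the minimal effective dose".

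**The concern.** Three features together look like a gap. The only power figure covers the trend, while the 20 mg and 10 mg arms have 50 patients each and come last in the sequence, so formal rejections there should be uncommon. The primary model works on ranks, so its least squares means are not in percentage points, and 9.4.2 does not say how a difference between arms will be expressed. The rule on nominal p-values is also lopsided: read literally, a trial that fails the trend test has a reporting rule for 10 mg, whereas a positive trial that stops at 20 mg has none.

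At stake is the use of the trial for dose selection. If 10 mg went unreported on the primary endpoint, a reader could not tell an ineffective dose from one measured imprecisely. It also looks odd that secondary endpoints have named estimators and the primary endpoint does not.

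**Working it through.** **Inputs.** Arms of 100, 50, 50 and 100 for placebo, 10, 20 and 25 mg (synopsis); the assumed medians (9.2); contrast -3, -1, 1, 3 and one-sided 0.05 at every step (9.1, 9.4.2). Variability is not stated, so the 88% cannot be reproduced independently. A common SD is solved from it instead, which matches 88% by construction.

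**SD implied by 88%.**
- Contrast: (-3)(-20) + (-1)(-25) + (1)(-30) + (3)(-35) = -50, so 50 points in favour of drug.
- Variance factor: 9/100 + 1/50 + 1/50 + 9/100 = 0.22; square root 0.469.
- SD = 50 / (0.469 × (1.645 + 1.175)) = 37.8 points. For trend power of 86% or 90% it would be 39.1 or 36.4.

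**Each comparison alone (one-sided 0.05).**

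| Dose | Difference | SE | Power |
|---|---|---|---|
| 25 mg | 15 | 37.8 × √(1/100 + 1/100) = 5.35 | 87.7% |
| 20 mg | 10 | 37.8 × √(1/50 + 1/100) = 6.55 | 45.3% |
| 10 mg | 5 | 6.55 | 18.9% |

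**The sequence.** Simulating the four arm means with a shared placebo gives cumulative rejection of 88.0% (trend), 84.4% (25 mg), 42.8% (20 mg) and 11.9% (10 mg). The trials end as follows:

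| Sequence ends | Share of trials | Doses not formally tested | Rule in 9.4.2 |
|---|---|---|---|
| H0123 not rejected | 12.0% | all three | nominal p-values for each dose |
| stops at H03 | 3.7% | 20 and 10 mg | none stated |
| stops at H02 | 41.6% | 10 mg | none stated |
| stops at H01 | 30.9% | none | not needed |
| all rejected | 11.9% | none | not needed |

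The two rows without a rule total 45.3% of all trials, or 51.4% of those that pass the trend test. For trend power of 86% to 90% the total runs from 45.6% to 44.6%. Negative binomial data analysed by rank ANCOVA (arm and baseline rank; theta 6 to 6.5 on 56-day counts; trend power 87% to 88.5%) give about 47%. The share is therefore stable to the assumed variability.

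**Precision for 10 mg.** The 95% half-width is 1.96 × 6.55 = 12.8 points. The interval contains both 0 and 15 when the estimate lies between 2.2 and 12.8. With a true difference of 5, that happens in about 55% of trials.

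**Would a 95% interval match the tests?** A two-sided 95% interval excludes 0 on the side of benefit with probability Φ(15/5.35 - 1.96), about 80%, for 25 mg, and Φ(10/6.55 - 1.96), about 33%, for 20 mg. The one-sided tests succeed in 88% and 45%. Some formally rejected doses would thus carry an interval that includes 0. A two-sided 90% interval matches the one-sided 0.05 test.

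**The case for a change.** The best argument for a change is that the protocol specifies less estimation for its primary endpoint than for its secondary ones, and that this matters most in the likeliest single outcome, a stop at 20 mg. RR50 dichotomises the percent change, and the exposure-response work in section 8.3.6 models concentration rather than randomised dose, so neither replaces a per-dose difference on the primary endpoint. Section 9.4.2 defers only additional sensitivity analyses to the SAP. Naming an estimator in advance would cost one sentence and would prevent a choice made after unblinding.

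The description of 9.4.2 stands: it names no between-arm estimate in percentage points, and its p-value rule does not reach a stop at H03 or H02. The consequence does not follow.

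- Section 9 presents itself as a summary and requires a SAP finalised before database lock; section 9.4.6 places unblinding after that lock. An estimator and a table layout are ordinary SAP content and can still be settled blind. Without the SAP, their absence from the whole plan cannot be shown.
- The three pairwise comparisons come from one fitted model, so a nominal p-value for 10 mg is available wherever the sequence stops. The gatekeeping limits formal claims, not description.
- The endpoint in section 3 is itself a median percent change, and 9.4.3 plans weekly percent change within each arm. The RR50 odds ratios with intervals do not depend on where the primary sequence stops, because 9.4.1 leaves secondary endpoints unadjusted.

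**Conclusion.** No change is needed. The power statement is accurate for the hypothesis that defines a positive study, and the fixed sequence protects the one-sided 0.05 level. Placing more patients in the placebo and 25 mg arms is an open trade-off in a Phase 2 dose-ranging trial. Publishing power for each step would alter neither the allocation, the order nor the error rate.

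What remains is unwritten reporting detail. On the back-solved SD of 37.8 points, it concerns 10 mg alone in about 42% of trials and both 20 mg and 10 mg in about 4%. Analysts would fill it by giving a difference from placebo and a nominal p-value for each dose, marked as descriptive beyond the stopping step. The trial's own simulation check already used the Hodges-Lehmann estimate, so the obvious choice is to hand.

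The stopping shares rest on the assumed SD and on the plan's medians being true, but they move little across the variants tried. The interval width is less certain: 12.8 points under the normal approximation, and about 16 to 17 with Hodges-Lehmann in a negative binomial simulation.

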9.3 POPULATIONS FOR ANALYSES

The analysis datasets will include the following:

- **ITT:** All randomized participants who received at least one dose of IMP during the DBP, and provided at least one record of post-treatment seizure frequency during the DBP. Participants will be analyzed as-randomized.
- **Per Protocol:** Participants analyzed according to product and dose received during the DBP, who completed at least 80% of all diary records for a minimum of 4 weeks during the DBP, complied with at least 80% of expected IMP administrations during the DBP, did not withdraw consent, terminate for administrative issues, or were otherwise lost to follow-up during the DBP.

- **Safety:** All participants who receive at least one dose of IMP during the DBP, analyzed according to product and dose received.
- **OLE Efficacy:** All participants entering the OLE who receive at least 1 dose of IMP following the DBP and who provide at least 1 month of diary data in the OLE. Participants will be analyzed as-treated.
- **OLE Safety:** All participants entering the OLE who receive at least 1 dose of IMP following the DBP. Participants will be analyzed as-treated.

9.4 STATISTICAL ANALYSES

9.4.1 GENERAL APPROACH

A basic frequentist approach will be taken with this analysis. Efficacy analyses will generally be 1-sided, 0.05-level tests. The primary efficacy endpoint may include multiple hypothesis tests, with study-wide type I error controlled through a closed-testing procedure. In this Phase 2 study, safety endpoints and secondary efficacy endpoints will not be adjusted for multiplicity across endpoints or arms. All analyses will be accompanied by graphical presentations of results including forest, line, and bar graphs.

9.4.2 ANALYSIS OF THE PRIMARY EFFICACY ENDPOINT(S)

The monthly (28 days) seizure rate will be calculated separately in the baseline and DBP as the total number of focal seizures reported \times 28 / the total number of days seizure information is available in that period. The countable seizures for the primary endpoint will include focal aware seizures with motor signs, focal seizures with impaired awareness with or without motor signs, and focal seizures that lead to generalized tonic-clonic seizures.

Percent change from baseline will be calculated as (post-treatment monthly [28 days] focal seizure frequency – baseline monthly (28 days) focal seizure frequency) / baseline monthly (28 days) focal seizure frequency, so that a more negative number will represent greater benefit.

Primary analysis to test the null hypothesis as described in [Section 9.1](#) is based on the ITT population. Since the endpoint of percent change from baseline in monthly seizure count tends to be not normally distributed, an analysis of covariance (ANCOVA) model for the ranks of monthly (28 days) focal seizure frequency percent change from baseline will be used as the dependent variable, with baseline monthly (28 days) focal seizure frequency rank, arm (placebo, 10 mg, 20 mg, 25 mg), region, and background use of CYP3A4 inducer medication included as factors.

Under the assumption of a monotonic dose response relationship (true effect for the higher dose is not worse than the lower dose), the null hypothesis (H_{0123} : $MPC_{plac} = MPC_{10mg} = MPC_{20mg} = MPC_{25mg}$) will be tested based on linear contrast for the least square means (with coefficient of -3, -1, 1, 3 for placebo and the 3 treatment levels of 10, 20, and 25 mg) within the framework of the ranked ANCOVA model. Since only a positive dose response trend is of interest to demonstrate treatment effect, a 1-sided test with significance level of 0.05 will be used.

If a significant result is achieved ($p < 0.05$) under H_{0123} , the study will be considered positive and at least one dose level of XEN1101 should be better than placebo.

After H_{0123} is rejected, further testing (with the same significance level of 0.05) will be performed to formally test the pairwise difference H_{03} : $MPC_{plac} = MPC_{25mg}$, H_{02} : $MPC_{plac} = MPC_{20mg}$ and H_{01} : $MPC_{plac} = MPC_{10mg}$.

MPC_{10mg} in sequential order ($H_{03} \rightarrow H_{02} \rightarrow H_{01}$) to assess whether each dose level is significantly better than placebo in percent reduction of monthly focal seizure count, within the same ANCOVA model. To control the type I error, only when the early null hypothesis is rejected, then the later hypothesis can be formally tested.

On the other hand, if the primary null hypothesis H_{0123} is not rejected, then additional formal statistical testing will not be performed. However, the nominal p-value comparing each of the doses versus placebo will still be provided for exploratory purposes.

With this a-priori specified stepwise testing procedure, the overall type I error will be controlled at 0.05 (1-sided).

Note that this study was designed as a Phase 2 study; therefore, 1-sided alpha of 0.05 was proposed to determine the efficacy of XEN1101. Further study will be needed to confirm the efficacy of XEN1101. It is the sponsor's understanding that in order for this study to be considered as a pivotal study, the 1-sided p-value will need to be <0.025 in favor of XEN1101.

Additional sensitivity analyses for the primary endpoint will be specified in the SAP.

